8.4 Efficacy Analysis

Primary Endpoint (Imaging): Comparison of Standardized Uptake Values (SUV_{max} and SUV_{mean}) of the primary tumor and representative metastatic lesions between baseline and 1-month post-treatment [18F]-FAPI PET/CT scans.

Background Reference: Mean SUV of normal liver tissue.

Secondary Endpoint (Biomarkers): Comparison of serum tumor marker levels pre- and post-treatment.

Statistical Test: Continuous variables (SUV, biomarker levels) will be tested for significant changes using the Paired t-test (if normally distributed) or Wilcoxon signed-rank test (if non-normally distributed).

A P-value < 0.05 will be considered statistically significant.

Data will be presented as Mean \pm SD or Median (Range).

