3.2 Secondary Objective

1. To preliminarily assess the therapeutic response of [177Lu]Lu-TEFAPI-06 in patients with FAP-high expressing tumors.

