5. STUDY POPULATION

5.1 Inclusion Criteria

1. Diagnosed with metastatic solid tumors via pathology.
2. Confirmed high FAP expression in tumor lesions via [18F]-FAPI PET/CT screening (Tumor uptake significantly higher than background).
3. Expected survival time > 3 months.
4. Voluntarily signed the informed consent form.

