7.2 Efficacy Assessment (Follow-up)

Timeline: Baseline (pre-treatment) and 1 month post-treatment.

Modality: [18F]-FAPI PET/CT.

Biological Markers: Tumor-specific serum markers will be measured at baseline and follow-up.

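### The SUV endpoint in 8.4 has no place for new lesions, so a fall in the followed lesions could be reported as response while new metastases on the same 1-month scan go unreported

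*Combined protocol and SAP*

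**What the plan says.** The efficacy aim is Section 3.2: "To preliminarily assess the therapeutic response of [177Lu]Lu-TEFAPI-06 in patients with FAP-high expressing tumors". Section 5.1 makes metastatic disease a condition of entry ("Diagnosed with metastatic solid tumors via pathology").

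Section 7.2 schedules the efficacy assessment at two times ("Baseline (pre-treatment) and 1 month post-treatment"), with one imaging method ("Modality: [18F]-FAPI PET/CT") plus tumor-specific serum markers.

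Section 8.4 turns the scans into an endpoint: SUVmax and SUVmean "of the primary tumor and representative metastatic lesions between baseline and 1-month post-treatment". SUV and marker levels are compared by paired t-test or Wilcoxon signed-rank test, and "A P-value < 0.05 will be considered statistically significant". Results are shown as group summaries.

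The plan does not say how, when or in what number representative lesions are chosen. It has no rule for new lesions, no definition of progression and no response criteria.

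**The concern.** In metastatic disease, a new lesion is among the most unfavourable findings that a follow-up scan can show. The planned measure looks only at uptake in lesions that have a baseline value. If uptake falls in those lesions while disease appears elsewhere, the planned imaging output shows only the fall.

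What is at stake is the reading of the secondary objective. A significant fall in SUV could be described as preliminary therapeutic response, and no planned table or listing would tell the reader that some of the same patients had new metastases on the same scan. Safety and dosimetry, the primary objectives, are not affected.

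**Working it through.** The plan has no figure to reproduce here: it gives no power, expected SUV change or response rate, and Section 8.1 sets N = 5 without a calculation. The check is whether a new lesion can reach any planned output.

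**Step 1. What enters the endpoint.** For each followed lesion or patient the paired quantity is d = SUV(1 month) − SUV(baseline). Both tests in 8.4 need both terms. A lesion that first appears at 1 month has no baseline lesion SUV, so d is undefined. Section 8.6 rules out imputation and uses observed data only. Nothing in 8.4 provides for reading background uptake at that site on the baseline scan. The new lesion is therefore outside the endpoint.

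**Step 2. Whether another section picks it up.**

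| Section | What it records | New lesions or progression? |
|---|---|---|
| 7.2 | PET/CT and serum markers at two times | Not mentioned |
| 8.2 | Analysis sets | Not mentioned |
| 8.3 | Dosimetry for organs and tumor lesions | Not mentioned |
| 8.4 | SUV of followed lesions; serum markers | Not mentioned |
| 8.5 | Adverse events and laboratory values | Progression not named |
| 8.6 | Missing data | Not mentioned |

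**Step 3. Direction.** A followed lesion that fades enters as a fall in SUV. A lesion that appears enters as nothing. For new lesions the omission can therefore only favour the drug. An existing lesion not chosen as representative may change more or less than the chosen ones, and the selection rule is not stated, so the direction there is unknown.

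**Step 4. Weight of a new lesion in the planned result.** This is an illustration; every SUV is assumed, with one value per patient.

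- Baseline: 12, 10, 15, 9, 11
- 1 month: 9, 8, 10, 7.5, 8
- d: −3, −2, −5, −1.5, −3
- Mean d = −14.5 / 5 = −2.9
- Sum of squared deviations = 0.01 + 0.81 + 4.41 + 1.96 + 0.01 = 7.20; SD = √(7.20 / 4) = 1.342
- t = −2.9 / (1.342 / √5) = −4.83 on 4 df; two-sided p = 0.008
- Exact two-sided Wilcoxon p = 2 / 2⁵ = 0.0625

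Let k be the number of patients with new metastases. It appears in none of these formulas, so the mean and both p-values are the same for k = 0, 1, 2, 3, 4 and 5. The weight of a new lesion is zero by the definition of the endpoint, and that conclusion does not depend on the assumed SUVs.

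**Step 5. Share of the sample.** One affected patient is 1/5 = 20%; two would be 2/5 = 40%. The documents give no expected rate of new lesions within 1 month, so k cannot be estimated.

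**The case against.** Several points on the other side are sound.

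- **No patient is classified.** A reader might infer that a patient with new metastases is counted as improved. The documents do not support that: Section 8.4 compares SUV as a continuous variable and defines no responder, improved or progressing category. The gap remains, because with no per-patient outcome no planned output would show the problem.
- **SUV is not the only efficacy information.** Serum markers are measured at both times and analyzed in 8.4, and they are not tied to the chosen lesions. They are a separate measure and do not replace a record of new lesions.
- **The bias is not one-sided throughout.** A reader might infer that everything left out flatters the drug. That holds for new lesions only. For existing lesions not chosen, the issue is selection, and a rule fixed at baseline would address it. Such a rule would still not capture a lesion that did not exist at baseline.
- **Silence is not prohibition.** The plan does not forbid the investigator from describing new lesions in the report. It does not require it either, so the decision would be made after the scans are seen.
- **This is a small pilot.** With N = 5, a mainly descriptive analysis and a response aim that is secondary and preliminary, the gap is not grave. Yet 8.4 still applies a significance threshold to this endpoint, and a descriptive study is well suited to a per-patient listing.

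**Conclusion.** The concern holds in limited form. The imaging endpoint gives new lesions zero weight and no other section records them. A fall in SUV in the followed lesions could be reported as preliminary therapeutic response while new metastases on the same 1-month PET/CT go unreported. A misleading result requires both that the followed lesions fall and that new lesions appear.

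The zero weight follows from the definition of the endpoint and needs no assumption. The practical size cannot be derived from the documents; all that can be said is that each affected patient is 20% of the sample if all five are evaluable. It would be tempting to go further and say that the trial will report response in patients who are progressing. The documents do not support this, since they define neither response nor progression and give no rate of new lesions.

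This is a cheap improvement that bears on the secondary objective only.

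**What to change.** In Section 8.4, add a per-patient listing read from the PET/CT already scheduled in 7.2. For each patient it should show the presence and number of new FAPI-positive lesions at 1 month, next to the SUV change in the followed lesions and the serum marker change. Add one sentence stating that a fall in SUV will not be described as therapeutic response for a patient with new lesions unless those lesions are reported alongside it.

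Total lesion count at both times may be added. Tumor volume and a binding progression category are optional and not needed to close the gap; volume would also need a segmentation rule that the plan does not have.

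The planned SUV comparison stays as it is. The cost is a few lines of SAP text and a little more reading time, with no extra scan or patient. The downside is that the efficacy result may look less favourable.

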8. STATISTICAL ANALYSIS PLAN (SAP)

8.1 General Considerations

This is a small-sample exploratory study (N=5). The statistical analysis will be primarily descriptive. No formal sample size calculation based on power analysis was performed due to the pilot nature of the study.

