8.2 Analysis Sets

Full Analysis Set (FAS):All participants who received the study drug and have at least one post-baseline efficacy evaluation.

Safety Set (SS):All participants who received the study drug.

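### Section 8.4 does not say whether an SUV pair is a patient or a lesion, and under neither reading does its test rule at P < 0.05 work as stated

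*Combined protocol and SAP*

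**What the plan says.** Section 8.4 (Efficacy Analysis) makes its main imaging endpoint the change in SUVmax and SUVmean of the "primary tumor and representative metastatic lesions between baseline and 1-month post-treatment" FAPI PET/CT scans. One sentence covers the test for both imaging and serum markers: "Continuous variables (SUV, biomarker levels) will be tested for significant changes using the Paired t-test", or the Wilcoxon signed-rank test if the data are not normal. The threshold follows: "A P-value < 0.05 will be considered statistically significant". Results are to be shown as mean ± SD or median (range).

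The text elsewhere that bears on the unit or on lesion choice is this:

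- Section 8.1 gives N=5 and says: "The statistical analysis will be primarily descriptive".
- Section 8.2 defines the Full Analysis Set by person: "All participants who received the study drug and have at least one post-baseline efficacy evaluation".
- Section 5.1 requires for entry: "Confirmed high FAP expression in tumor lesions via [18F]-FAPI PET/CT screening".
- Section 7.2 gives the two scan times and the modality.
- Section 8.3 describes regions of interest, but for SPECT/CT dosimetry only.
- Section 8.6 rules out imputation.
- Section 4 describes an open-label study, and no section describes a masked read.

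No section states the unit of the pair, the number of lesions per patient, how several lesions in one patient are combined, or when and by what rule the representative lesions are chosen.

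**The concern.** Both named tests assume independent pairs. Lesions in one patient share one injection and the same two scans, so their changes may well move together. A table of lesion pairs run through either test would then overstate the information in 5 patients and give a P-value that is too small.

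Taking one value per patient removes that problem and exposes another. With 5 pairs the Wilcoxon test has too few possible outcomes to reach 0.05.

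The choice of unit therefore decides which part of the stated rule fails, and the plan leaves that choice open.

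The second gap is the timing of lesion choice. Screening PET/CT shows the lesions before dosing, but nothing says a list is fixed then. If lesions are picked once the 1-month scan is visible, the picking can be influenced by the result. Unlike the pooling problem, this would also distort the descriptive mean and median.

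**Working it through.** **Inputs.** From the documents: 5 patients, two scans, paired t-test or Wilcoxon test, threshold 0.05. The plan states no power, SD, lesion count or correlation, so it has no figure of its own to reproduce. Assumed: two-sided testing (section 8.4 does not state sidedness), 2 to 5 lesions per patient, and within-patient correlation of lesion changes from 0 to 0.8.

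**Readings the text allows.** (1) One combined value per patient. (2) The primary tumor tested alone, one pair per patient. (3) All lesion pairs pooled. Readings 1 and 2 behave alike below.

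**Step 1: pooled lesions.** With m lesions in each of 5 patients, M = 5m, lesion-change variance s² and correlation r:

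- true variance of the mean = (s²/M) × [1 + (m − 1)r]
- average variance estimate used by the test = (s²/M) × [M/(M − 1)] × [1 − (1 + (m − 1)r)/M]

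Example, m = 3 and r = 0.5: M = 15 and 1 + 2 × 0.5 = 2. The true variance is 2 × s²/15. The test uses (15/14) × (1 − 2/15) = 0.929 times s²/15. The standard error is therefore too small by a factor of √(2/0.929) = 1.47. The critical value 2.145 (14 df) acts like 2.145/1.47 = 1.46, which gives a false-positive rate of about 17%. Simulation gives 17.6%.

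Simulated false-positive rates (%) of the pooled t-test, with no true change and 200,000 trials per setting:

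| Lesions per patient | r = 0 | 0.1 | 0.3 | 0.5 | 0.8 |
|---|---|---|---|---|---|
| 2 | 4.9 | 6.1 | 8.5 | 11.3 | 16.4 |
| 3 | 5.0 | 7.1 | 12.3 | 17.6 | 25.6 |
| 4 | 5.0 | 8.5 | 15.7 | 23.2 | 32.7 |
| 5 | 4.9 | 9.7 | 19.1 | 27.5 | 38.2 |
| 1, 1, 2, 3, 5 | 5.0 | 7.4 | 13.1 | 19.1 | 28.3 |

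The pooled exact Wilcoxon test behaves alike: 8% to 18% at r = 0.3 and 15% to 35% at r = 0.8, for 2 to 5 lesions each.

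**Step 2: one value per patient.** The t-test on patient means rejects in 4.9% to 5.1% of null trials with equal lesion counts and in 4.2% to 5.0% with uneven counts, so it is valid. For the exact two-sided Wilcoxon test, the smallest P arises when all n changes have the same sign: 2/2^n. With n = 5 this is 2/32 = 0.0625. With n = 4 (one patient without a 1-month scan, no imputation) it is 2/16 = 0.125. Neither is below 0.05. Six pairs would give 2/64 = 0.031, so pooling lesions could supply a significance that patient values cannot.

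The word *exact* matters. The large-sample approximation without continuity correction gives, at n = 5, z = 7.5/√13.75 = 2.02 and P = 0.043. Software that defaults to it could report significance, but the approximation is not reliable at n = 5: the exact P for the same data is 0.0625.

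**Step 3: late lesion choice.** The model is one mean per patient with no true change, where 2 of 4 lesions are kept. The nominal rate of significant falls is 2.5%.

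- Chosen without regard to the change: 2.5% significant falls (r = 0.5).
- Chosen as the two largest falls: 26%, 17% and 8% at r = 0.3, 0.5 and 0.8. With an assumed lesion log-change SD of 0.2, the mean apparent change is −10.5%, −9.0% and −5.8%.

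Higher correlation raises the pooling error and lowers the selection error, so the two must not be added.

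**The case against.** The patient-level reading has the better textual support. N is 5, the analysis set is made of participants, and the same test sentence covers serum markers, which give one value per patient at each time. No text favors pooling. A reader might infer that the plan intends to pool lesions and that its P-value is therefore invalid. The documents do not support that. They leave pooling open, and the inflation also needs several lesions per patient and positive correlation, neither of which they quantify. What remains is that section 8.4 lists several lesions per patient with no combining rule, so even the patient-level reading needs an unstated choice, and under it the Wilcoxon branch fails.

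A reader might also infer that responding lesions will be picked. The documents do not support that either: choosing lesions because they fell most is hard to square with calling them representative. Late choice alone does no harm, as Step 3 shows, and the largest-fall figures are an extreme case. What remains is an avoidable opening in an open-label study.

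The Wilcoxon floor comes from having 5 patients, not from leaving the unit undefined. That is right, and it is not a cost of the fix. It belongs here because it shows that settling the unit does not by itself make the stated rule work.

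Finally, the stakes are low. The analysis is mainly descriptive, efficacy is a preliminary secondary objective (section 3.2), and no decision depends on this P-value. That limits the weight, but section 8.4 still sets a significance threshold.

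**Conclusion.** The point holds as an ambiguity with a consequence under either reading. Pooled lesions give a false-positive rate above 5% whenever changes are positively correlated within patients: about 8% to 19% at correlation 0.3 and 16% to 38% at 0.8. One value per patient keeps the t-test at about 5% but leaves a Wilcoxon branch that cannot meet P < 0.05. The pooling figures rest on assumed lesion counts and correlations. The Wilcoxon result rests only on 5 patients and an exact two-sided test, which the SAP does not specify.

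The open timing of lesion choice is a separate and weaker point. It matters only if the outcome influences the choice, and the documents give no basis for saying how much it would. The plan should be corrected, but the trial's primary objectives, safety and dosimetry, are untouched.

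**What to change.** In section 8.4:

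1. State that the patient is the unit of analysis for SUV change.
2. List the lesions on the baseline scan before dosing by a complete fixed rule, for example all lesions above a stated uptake and size limit, including the primary if present. Measure the same lesions at 1 month.
3. Average the change within patient. A log-ratio scale is optional.
4. Report the 5 patient values with their mean and 95% CI, show individual lesions descriptively, and label any P-value exploratory.
5. Drop the Wilcoxon test for this endpoint, or state that its exact two-sided P cannot reach 0.05 with 5 patients.

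Avoid a rule based only on the highest uptake, which invites regression to the mean. Some of that may remain in any case, since patients enter on high uptake at screening and the documents do not say whether that scan also serves as baseline.

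The cost is SAP wording and a baseline lesion list, with no extra scans. The 95% CI is wider than a pooled one. With 2 to 5 lesions each, it is 1.2 to 1.3 times as wide at correlation 0, 1.5 to 2.3 times at 0.5 and 1.7 to 2.9 times at 0.8. Where lesions are correlated, much of the pooled interval's apparent precision is not real.

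### Section 8.4 puts no baseline condition on serum markers, so any patient whose marker is normal at baseline would dilute the pre/post marker comparison

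*Combined protocol and SAP*

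**What the plan says.** Section 7.2 states: "Tumor-specific serum markers will be measured at baseline and follow-up". It names no marker and sets no condition on the baseline value. Section 8.4 makes the secondary efficacy endpoint "Comparison of serum tumor marker levels pre- and post-treatment" and adds: "Continuous variables (SUV, biomarker levels) will be tested for significant changes using the Paired t-test", with the Wilcoxon signed-rank test as the alternative when the data are not normal. The threshold follows: "A P-value < 0.05 will be considered statistically significant". Results are shown as mean and SD, or median and range.

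Two rules decide who enters. Section 8.2 defines the full analysis set as "All participants who received the study drug and have at least one post-baseline efficacy evaluation", and section 8.6 uses observed data without imputation. Neither mentions the marker level.

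Eligibility does not supply the condition either. Section 5.1 requires "Diagnosed with metastatic solid tumors via pathology" and enriches on FAPI PET uptake only. Section 5.2 has no serum-marker criterion. The documents give no upper limit of normal for a marker, no marker-evaluable subset and no definition of marker response.

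**The concern.** A marker that is already normal before treatment has little room to show a treatment-related fall. If such patients are compared together with patients whose marker is raised, two things happen: the average change shrinks, and the spread between patients grows because fallers and non-fallers are mixed. Both lower the paired t statistic. This would be so even if all five patients had the same marker in the same unit.

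The marker is the only planned efficacy measure that does not rest on FAPI PET. A flat pooled result could be read as failing to support the PET finding even if every patient with a raised marker had responded. If normal-baseline patients were instead set aside after the results were seen, the choice would be open to selection. A rule fixed beforehand avoids both.

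**Working it through.** **Inputs from the documents.** Five patients, single arm (sections 1 and 8.1). Paired t-test or Wilcoxon signed-rank test at 0.05 (8.4); sidedness is not stated, so two-sided is assumed. There is no planned power or effect size to reproduce: "No formal sample size calculation based on power analysis was performed due to the pilot nature of the study".

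**Assumptions, not in the documents.** k of the 5 patients are raised at baseline. Raised markers halve and normal markers do not change on average. The log change has noise SD 0.15.

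**Step 1: mean change.** If the raised patients change by D on average and the others by about 0, the mean over five is kD/5. That is 80%, 60% and 40% of D for k = 4, 3 and 2.

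**Step 2: the t statistic without noise.** With k changes of D and 5−k zeros, the sample variance is D²·k(5−k)/20. So t = (kD/5) / √[D²·k(5−k)/100] = 2√[k/(5−k)].
- k=2: 2√(2/3) = 1.63
- k=3: 2√(3/2) = 2.45
- k=4: 2√4 = 4.00

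The two-sided 5% critical value on 4 degrees of freedom is 2.78. D cancels, so in this noise-free case a larger effect does not bring k=2 or k=3 to significance. The normal-baseline patients set the limit.

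**Step 3: with noise, log values.** 200,000 simulated trials; share with P<0.05:

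| k raised | all 5 patients | raised only |
|---|---|---|
| 2 | 2.4% | 39% |
| 3 | 23% | 96% |
| 4 | 89% | more than 99% |

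**Step 4: raw levels, the scale that 8.4 names.** Further assumptions: normal markers at 0.5 times the upper limit, and raised markers with median 3 times the limit and log baseline SD 0.7. With k=3, P<0.05 is reached in 0.2% of trials on all 5 patients, against 29% on the raised patients only. The loss is therefore not a product of the log scale.

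**Step 5: different assumptions.** Let the raised patients change by 2 SD, and let the SD in normal-baseline patients be 0.2 or 1.0 times that in raised patients. Paired t power on all five is 0.91 at k=5, 0.52–0.62 at k=4, 0.03–0.22 at k=3 and 0.00–0.09 at k=2. On raised patients only it is 0.76, 0.47 and 0.18 at k = 4, 3 and 2. For changes of 1 to 3 SD, the raised-only analysis had the higher power in every scenario with k<5, despite fewer patients.

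**Step 6: the Wilcoxon branch.** The smallest exact two-sided P is 2/2⁵ = 0.0625 at n=5 and larger at smaller n. That branch cannot reach 0.05 whichever patients are included.

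**Step 7: cost of selecting raised baselines.** Assume a within-patient log SD of 0.1, and true log levels centred on the upper limit with SD 0.7. The expected spurious fall in selected patients is 0.1²/√(0.7²+0.1²) × 0.798 = 0.011, or about 1%.

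**The case against.** **The dilution is conditional.** That every patient is compared is inferred from the absence of any restriction; 8.4 does not say so. The documents do not say how many patients will have a normal baseline, and if none do the effect is zero. A reader might infer that dilution is certain, but the text supports only that nothing prevents it. This stands.

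**The reported percentage fall need not shrink much.** A reader might infer that a true 50% fall would appear as 13%, 24% or 34% with one, two or three raised patients. Those figures come from a geometric mean ratio, 0.5^(k/5), which is not the plan's statistic: 8.4 compares levels and reports mean and SD, or median and range. On raw levels a normal marker is small and adds little to the mean. With normal markers at 0.5 times the upper limit, the arithmetic mean falls 30%, 40% and 45% when raised markers sit at 3 times the limit, and 42%, 47% and 48% at 10 times. This stands. What shrinks to k/5 is the mean absolute change, and the t-test still loses power.

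**A normal marker is not uninformative.** A reader might conclude that it says nothing about response. It can still rise, and a rise may mean progression. Dropping such patients would keep those with room to fall and hide those who can only worsen. With no control arm, selecting raised baselines also adds regression to the mean toward apparent benefit. This stands as a condition on the fix: normal markers must stay visible, with rises reported beside the summary.

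**Little depends on the test.** Section 8.1 makes the analysis mainly descriptive, response is a secondary objective (3.2), and no decision rule uses the marker P-value. This lowers the priority. It does not remove the point, because 8.4 still applies a significance threshold and the reported mean absolute change is itself diluted.

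**Conclusion.** The point holds conditionally. As written, every full-analysis-set patient with an observed pair enters the marker comparison, because no section sets a baseline condition. If k of 5 patients are raised and the rest do not move, the mean absolute change is about k/5 of that in the raised patients. Under halving and log noise SD 0.15, the test on log values reaches P<0.05 in 2.4% (k=2) and 23% (k=3) of trials on all five patients, against 39% and 96% on the raised patients only. The exact rates depend on those assumptions and on a scale that the plan does not use, but the direction is the same on raw levels and under the other assumptions tried.

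The documents do not support the claim that dilution will occur, that the reported percentage fall will shrink in the same proportion, or that the trial's main conclusions are at risk. This is an improvement to consider in a secondary, descriptive endpoint.

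**What to change.** In section 8.4, replace the marker comparison with wording such as:

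*Marker response is summarised descriptively, without a P-value, as each patient's ratio of 1-month to baseline, for markers above the laboratory's upper limit of normal in the pre-injection baseline sample, with the number evaluable. Markers normal at baseline are listed for every patient as not evaluable for a fall, and any rise above the upper limit is reported beside the summary as possible progression.*

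The test sentence in 8.4 should then no longer cover biomarker levels. This also removes the question of which test to run when only one or two patients are evaluable. A per-patient ratio has no unit, so it can be listed across different markers. Naming the markers for each tumour type is a separate matter that this wording does not settle.

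The cost is a few sentences; the baseline sample is already planned and every value is still reported. The summary may contain fewer than five patients. Selecting raised baselines brings slight regression to the mean toward apparent benefit, about 1% under the assumptions in step 7. With a single arm this cannot be separated from a treatment effect, so it should be stated with the result.

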1. STUDY SYNOPSIS

Study Phase: Exploratory (Phase 0/I)

Investigational Product:[177Lu]Lu-TEFAPI-06

Indication: fibroblast activation protein (FAP)-high expressing metastatic solid tumors

Methodology: Open-label, single-center, single-arm study

Sample Size: 5 participants

Intervention:Single intravenous injection of approx. 20 MBq/kg [177Lu]Lu-TEFAPI-06.

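### Section 8.4 analyses serum tumor markers as raw levels; the documents permit different markers across the five patients, and if these are pooled the results depend on each laboratory's reporting unit.

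*Combined protocol and SAP*

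**What the plan says.** Section 8.4 defines the secondary efficacy endpoint as "Comparison of serum tumor marker levels pre- and post-treatment". It then gives one recipe for all efficacy variables. "Continuous variables (SUV, biomarker levels) will be tested for significant changes", by "Paired t-test (if normally distributed) or Wilcoxon signed-rank test (if non-normally distributed", with the threshold "A P-value < 0.05 will be considered statistically significant". The summary format begins "Data will be presented as Mean" and gives SD, or median with range, as its companions. Section 8.4 mentions no ratio, percent change, log scale, per-marker analysis or pooling rule.

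Three other sections bear on which markers will be present. The indication in section 1 is "fibroblast activation protein (FAP)-high expressing metastatic solid tumors". The first inclusion criterion in section 5.1 is "Diagnosed with metastatic solid tumors via pathology", with no histology specified. Section 7.2 says "Tumor-specific serum markers will be measured at baseline and follow-up", in the plural, naming neither marker nor unit.

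Section 3.2 makes therapeutic response a secondary and preliminary objective. Section 8.1 describes the analysis as mainly descriptive, with N = 5.

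**The concern.** A level has a unit. If one patient's marker is reported in ng/mL and another's in pg/mL, or if they are different markers altogether, an average of the five levels has no interpretable unit. The patient whose number happens to be largest dominates it. The paired t-test works on differences of levels and inherits the same weighting. So does a normality check on those differences, and with it the choice of test. The Wilcoxon test ranks the absolute differences, so it too is affected once patients move in different directions.

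At stake is whether the reported change in markers, its direction and its P-value describe the patients or the reporting conventions of the laboratories.

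**Working it through.** **Inputs.** From the documents: N = 5 (sections 1 and 8.1); raw levels, the two tests and P < 0.05 (section 8.4); no imputation, so at most five pairs (section 8.6). The documents give no marker values, effect size or SD, so there is no plan figure to reproduce and every marker value below is assumed. Also assumed, because section 8.4 is silent: two-sided tests, and Shapiro-Wilk P > 0.05 on the differences selects the t-test.

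**Formulas.** With d = post − pre, t = mean(d) / (SD(d)/√5) on 4 df. The Wilcoxon P is exact, over all 2^5 = 32 sign patterns.

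**Response pattern for both examples.** Four patients halve (ratio 0.5) and one rises by half (ratio 1.5). In any unit, the geometric mean ratio is (1.5 × 0.5^4)^(1/5) = 0.62 and the Wilcoxon P on log ratios is 0.125.

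**Example 1: the unit enlarges the riser.** The other baselines are 40, 12, 60 and 100. The riser's baseline is 8 ng/mL, or the same value written as 8000 pg/mL.

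| | Riser in ng/mL | Riser in pg/mL |
|---|---|---|
| Differences | 4, −20, −6, −30, −50 | 4000, −20, −6, −30, −50 |
| Mean level, pre to post | 44.0 to 23.6 (−46%) | 1642 to 2421 (+47%) |
| Median level, pre to post | 40 to 20 | 60 to 30 |
| Mean (SD) of d | −20.4 (21.0) | 778.8 (1800.8) |
| t, P | −2.17, 0.096 | 0.97, 0.39 |
| Wilcoxon P | 2 × 2/32 = 0.125 | 2 × 10/32 = 0.625 |
| Shapiro-Wilk P, test selected | 0.94, t-test | 0.0002, Wilcoxon |

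The direction of the mean and the selected test both change. The 0.05 verdict does not.

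**Example 2: the unit shrinks the riser.** The other baselines are 40, 60, 80 and 100. The riser's baseline is 30 pg/mL, or the same value written as 0.03 ng/mL.
- At 30: mean d = −25.0, SD 25.0, t = −2.24, P = 0.089.
- At 0.03: mean d = −28.0, SD 19.2, t = −3.25, P = 0.031.
- Shapiro-Wilk P is 0.55 and 0.93, so the t-test is selected both times and the verdict crosses 0.05. The Wilcoxon P is 0.125 both times.

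This crossing depends on the baselines chosen. It needs a riser baseline of at least 13 (t P = 0.0511); at 12, P is already 0.0493. With the other baselines of Example 1, shrinking the riser 1000-fold moves the t P only from 0.096 to 0.076, and nothing crosses.

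**How often the verdict changes.** The same response pattern was simulated with log-normal baselines (median exp(4)), log-normal noise of SD 0.15 on the ratios, and the riser rewritten 1000-fold.
- Riser written smaller: the verdict changes in about 65% of draws at baseline log-SD 0.5, 18% at 1.0, 6% at 1.5, and 2–3% at 2.
- Riser written larger: the verdict changes in only 1–2% at log-SD 0.5 to 1.5, but the sign of the mean change reverses in about 98%, 92% and 87% of draws.

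**Where units do not matter.**
- One common factor applied to all five patients leaves every P unchanged.
- If all five changes have the same sign, rescaling cannot reverse the sign of the mean, and the exact Wilcoxon P is 2 × (1/2)^5 = 0.0625 in any unit.
- If each marker is tested separately in one unit, the unit cancels in the P-value.

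**The case against.** The defect needs two conditions that the documents do not state: patients with different markers, and an analyst who pools them. Section 8.4 speaks of continuous variables and levels in the plural, so each marker may well be meant as its own variable, as SUVmax and SUVmean are. That stands. A reader might infer that the plan will pool unlike markers. It does not say so; it only leaves the choice open.

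The numbers are also fragile. The 65% figure uses log-SD 0.5, which puts about 95% of baselines within exp(1.96 × 0.5) = 2.7-fold of the median. That is a tight spread for supposedly different markers, and wider spreads bring the figure close to zero. The sign reversal needs a patient who moves against the rest. Both limits stand, and neither figure should be read as a likely error rate.

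A reader might also argue that the per-marker route fails because a few pairs cannot reach P < 0.05 by exact Wilcoxon. That does not support this point. The minimum P is 2 × (1/2)^n, still 0.0625 at n = 5, so the limit holds for every n up to five, pooled or not, and a ratio scale does not remove it.

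Finally, the study is descriptive, and nothing in the documents ties a decision to the biomarker P-value. This limits the consequence. It does not answer the point fully, because the mean, SD, median and range are the descriptive output, and they depend on units too.

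**Conclusion.** The concern holds conditionally. Section 8.4 applies a raw-level method to an endpoint for which the documents permit different markers in different units. If these are pooled, the summaries have no interpretable unit. The direction of the mean, the selected test and the t-test P can then turn on how one laboratory reports, as can the Wilcoxon P when directions are mixed. That follows from the form of the statistics and needs no assumed data.

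The size does rest on assumed data. A swing from −46% to +47% is possible with one discordant patient. A change in the 0.05 verdict ranges from common with tightly clustered baselines to rare with widely spread ones.

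The documents do not support a claim that the planned analysis is wrong as it will be run: if all five patients share one marker and unit, there is no problem. Importance is minor, since this is a secondary efficacy endpoint in a primarily descriptive study of five patients.

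**What to change.** In section 8.4:
- Name the marker(s) for each patient before dosing. If a patient has several, state which one enters any summary.
- Make a per-patient listing the main result: marker, unit, baseline value and 1-month value, for every marker measured.
- Replace the analysis of raw levels with each patient's post/pre ratio or percent change.
- Report no mean, SD, median, range or P-value of raw levels across different markers. Label any geometric mean ratio across patients as descriptive.
- If all patients share one marker and unit, say so; raw summaries may then stay.

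The cost is a few sentences in the SAP and one baseline entry per patient, with no new samples or visits. The downside is that a ratio across patients still averages over different markers, which is why the listing comes first.
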